### 3.3 STUDY DESIGN

### 3.3.1 Study design

Stable HM3 patients who have not suffered a Major hemocompatibility-related adverse event after index hospitalization discharge and are at least 3 months postimplant will be screened for participation in the study. Upon meeting the study criteria and patient informed consent, the individuals will be randomized to either continued therapy with a Vitamin K antagonist and aspirin or conversion to apixaban 5 mg twice a day in a 2:1 manner (dose targeted to renal function); the apixaban group will be stratified further by 1:1 randomization to continued use of 100 mg aspirin once daily or cessation. Thus, 45 patients are planned to be enrolled and randomized in 3 subgroups of 15 patients in each arm (see Appendix I). After 180 days follow-up is reached, the Vitamin K antagonist and aspirin arm will be transitioned to apixaban and randomized in a 1:1 manner to groups with or without aspirin.

### 3.3.2 Adverse events adjudication and outcomes assessment

All suspected or confirmed HRAEs (safety surveillance see Appendix IV) will be promptly reported to and adjudicated by the Expert Advisory Committee to determine individual patient safety to continue with the assigned treatment arm and the overall study safety and eligibility for continuation. All adverse events will be periodically reported to the Institutional Ethics Committee.

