### 2 STUDY OBJECTIVES

#### 2.1 PRIMARY ENDPOINT

The primary endpoint to evaluate the safety and feasibility of apixaban with the HeartMate 3 LVAS is survival free of major HRAEs (hemocompatibility related adverse events) at 90 days post-enrollment. The primary analysis will compare the apixaban groups (n=30) to control (n=15). A separate analysis will compare the primary endpoint in patients randomized to receive aspirin (n=15) and no-aspirin (n=15) within the apixaban group.

Major HRAEs include:

- Stroke (ischemic/hemorrhagic)
- Pump thrombosis
- Severe bleeding (see Appendix II)
- Peripheral arterial thromboembolic events

HRAEs are influenced by several patient-specific risk factors, including anticoagulation, poor general health, altered circulation, the pump's hemocompatibility, and the presence of other comorbidities (e.g., AF, infections, etc.). In standard use, clinicians balance the risk of stroke and other thromboembolic (TE) events with the increased risk of bleeding when prescribing

anticoagulation or antiplatelet medications. Therefore, a composite endpoint comprising TE, bleeding, and pump-related events were chosen for the analysis.

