### 3 STUDY DESIGN

A prospective, single-center, randomized controlled trial of the feasibility and safety of apixaban in HeartMate 3 patients.

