#### 5.2.4.1 Apixaban plasma concentration

Apixaban peak and trough levels will be performed using a commercially available anti-Xa assay with apixaban calibrators at 4 weeks visit per study protocol. Levels will also be drawn at the time of presentation with any HRAE.

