#### Appendix I: Study design flow chart

### Appendix II: Severe Bleeding Definition

#### SEVERE BLEEDING:

Type A: (Meets any of the below)

- Overt bleeding plus hemoglobin drop of 3 to < 5 g/dL(30-50g/L) (provided hemoglobin drop is related to bleed)
- Any transfusion with overt bleeding

Type B: (Meets any of the below)

- Overt bleeding plus hemoglobin drop 5 g/dL (50g/L) or greater (provided hemoglobin drop is related to bleed)
- Cardiac tamponade
- Bleeding requiring surgical intervention for control (excluding dental, nasal, skin, or hemorrhoid)
- Hypotension attributable to bleeding and requiring intravenous vasoactive agents for hemodynamic support
- Intracranial Hemorrhage that does not meet the definition of hemorrhagic stroke

Type C1: Probable fatal bleeding; no autopsy or imaging confirmation but clinically suspicious

Type C2: Definite fatal bleeding; overt bleeding or autopsy or imaging confirmation

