symptoms?					х
Collect laboratory tests listed					
above					Х
Current anticoag/antiplt					
medications					Х
Any change to anticoag/antiplt					
meds? If yes, what					Х
Infection requiring antibx or + BC					Х
Describe event and treatment					х
Resolution date					Х
Other AE					
Onset date					х
Type of event					х
Examination incl. imaging					
methods					Х
Laboratory tests					х
Rehospitalisation/reoperation					х
Treatment					х
Outcome					
Date					Х

	Baseline	At regular ambulatory visits	Once a week	Once a month	At time of event
Type of outcome (expired,					
explanted, transplanted)					х
If expired, cause of death					х

LDH assessment once a week for 4 weeks, then once every 2 weeks for the next month and monthly thereafter

 ECHO follow–up will be performed at baseline, at 1 month and at 3 months, followed by periodical 6-monthly examinations

 Performed at 4 weeks visit after the anticoagulation transition in patient on apixaban only

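### Judgement-dependent primary-endpoint events go to the committee that also decides on continuing the assigned arm, and no masked classification is described

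*Protocol*

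**What the plan says.** Protocol Section 3.3.2 sends suspected and confirmed HRAEs to a single body. They are to be "promptly reported to and adjudicated by the Expert Advisory Committee to determine individual patient safety to continue with the assigned treatment arm", and the sentence goes on to add "and the overall study safety and eligibility for continuation". Event adjudication, the continuation decision for the individual patient and the judgement on the whole study therefore sit with one committee.

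The adjudicated events carry the primary endpoint, which Section 2.1 gives as "survival free of major HRAEs (hemocompatibility related adverse events) at 90 days post-enrollment". Stroke, pump thrombosis, severe bleeding and peripheral arterial thromboembolism are its non-death components.

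On masking:

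- Section 3 labels the study "A prospective, single-center, randomized controlled trial of the feasibility and safety of apixaban in HeartMate 3 patients" and says nothing about blinding.
- Section 3.3.1 randomizes patients to "continued therapy with a Vitamin K antagonist and aspirin or conversion to apixaban 5 mg twice a day", with aspirin then continued or stopped in the apixaban group. No placebo or dummy is described.
- The SAP adds only that an oversight committee assesses outcomes for clinical safety.

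The event record reveals the arm. On apixaban concentrations, Section 5.2.4.1 states: "Levels will also be drawn at the time of presentation with any HRAE". The HRAE block of Appendix III records "Current anticoag/antiplt" medications, and the laboratory block collects INR, aPTT, the Verify-now test and apixaban anti-Xa at the event.

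**The concern.** Deciding whether a patient may stay on the assigned arm requires knowing the arm. If the same people, in the same review, decide whether the episode counts as a major HRAE, that knowledge is available to them when they classify it. The plan provides no step in which classification is made without it.

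This matters for the components that need judgement. Under Appendix II an assessor must decide whether bleeding was overt, whether a hemoglobin fall is attributable to it, and whether a death without autopsy or imaging was probably from bleeding (Type C1). A suspected pump thrombosis also needs judgement: Appendix IV asks the team to exclude other explanations for a rise in LDH. All-cause death leaves almost no such room.

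At stake is the primary comparison of proportions, 30 against 15, where each event carries visible weight. Classification also affects follow-up, since Section 3.2 makes extension to 180 days depend on the patient being free of primary-endpoint events.

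**Working it through.** **Plan's own figure.** The SAP gives 45 patients. The allocation reproduces: 45 × 2/3 = 30 apixaban, 45 × 1/3 = 15 control, 30 / 2 = 15 per aspirin subgroup. The 45 itself cannot be reproduced, because no alpha, power, event rate, effect size or margin is stated. The point does not depend on it.

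**Weight of one event** (group sizes from Protocol Section 2.1).

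- Pooled apixaban: 1/30 = 3.3 percentage points.
- Control, or either aspirin subgroup: 1/15 = 6.7 points.

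**Two opposite shifts.** The documents give no expected event rate, so these counts are assumptions. Start from equal proportions, 2/15 control and 4/30 apixaban (13.3% each, difference 0).

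- Add one control event and remove one apixaban event: 3/30 − 3/15 = 10.0% − 20.0% = −10.0 points (two-sided Fisher p = 0.38).
- Reverse both shifts: 5/30 − 1/15 = 16.7% − 6.7% = +10.0 points. The documents do not favour either direction.

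**Fragility near a conventional threshold** (assumed counts). Control 4/15 against apixaban 2/30 gives Fisher p = 0.157. Removing one apixaban event (4/15 against 1/30) gives p = 0.036. Adding one control event (5/15 against 2/30) gives p = 0.032. The plan names no test or significance level for the primary comparison, so these values only show how much one event can matter.

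**Unequal recognition of events.** Suppose both arms share a true risk r, control events are all recognised, and apixaban events are recognised with sensitivity s. The spurious difference is r × s − r = −r(1 − s).

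| True risk r (assumed) | s = 0.9 | s = 0.7 |
|---|---|---|
| 5% | −0.5 points | −1.5 points |
| 30% | −3.0 points | −9.0 points |

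The distortion is small if events are rare and substantial if they are common. Swapping the arms changes the sign.

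**The case against.** **The committee needs the arm to protect patients.** True of the continuation decision, but classification against written definitions does not need it. What stands is a constraint on the remedy: Section 3.3.2 calls for prompt reporting, and a rule that classification must be locked before the arm is disclosed could hold up an urgent decision. It would also fail for a second event in a patient whose arm the members had already learned.

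**The definitions limit discretion.** Partly right. Death, the numeric hemoglobin thresholds and the INTERMACS definitions (Section 5.2.5) leave less room, so the exposure is confined to the judgement-dependent components.

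**This is a small feasibility study with no stated decision threshold.** Also fair. It limits the consequence, and the size depends on event rates that the documents do not give.

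**Stronger readings that the documents do not support.**

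- A reader might infer that the trial is declared open-label and that the committee is shown the arm when it classifies. The supplied text says neither, and it does not set out what the committee sees or in what order. The supportable statement is that no masking is described and that one of the committee's decisions requires the arm.
- A reader might infer that the results will favour apixaban. Nothing shows actual bias or its direction.
- A reader might infer that any bias would be irrecoverable. Section 7.3 keeps source documents at the site and Appendix III records laboratory values, imaging and event descriptions, so a later masked re-adjudication remains possible.
- A reader might infer that masked classification would cure all bias from knowledge of treatment. It cannot: a clinician's decision to transfuse, or to report a suspicion, is made at the bedside and reaches any assessor as a fact.

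**Conclusion.** The point holds as a risk of classification bias at the primary endpoint. One committee both adjudicates the non-death components and rules on continuing the assigned arm, the event record contains several arm-revealing items, and no masked classification is described.

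The firm size is 3.3 points per reclassified event in pooled apixaban and 6.7 points in control or an aspirin subgroup. The 10-point shift, the p-values and the sensitivity figures rest on assumed event counts, risks and recognition rates. The conclusion assumes that the removed pages do not describe masking. A change is worthwhile because it is cheap and leaves the sample size and the clinical rules alone. The gap does not invalidate the design.

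**What to change.** Amend Protocol Section 3.3.2 to separate the two tasks, and refer to the change in the SAP.

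1. Leave the prompt, unmasked safety and continuation review as it is. It does not wait for anything below.
2. In parallel or afterwards, have designated existing committee members who take no part in that patient's continuation decision classify every referred event, suspected or confirmed, against the written definitions.
3. Give them a packet with arm, antithrombotic drug names, INR, aPTT, anti-Xa, Verify-now and reversal-agent details removed. Verify-now belongs on the list because a platelet-function test could reveal aspirin status, and reversal details because Appendix V is specific to apixaban.
4. Lock that classification and state in the SAP that the primary analysis uses it.

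The cost is protocol and SAP wording plus some redaction per event. No new committee is needed, provided the present one has enough members to divide the work; its size is not given. Masking will sometimes be imperfect, because a narrative can give the drug away. The change reduces classification bias and leaves bias from unmasked transfusion decisions and unmasked reporting of suspicion in place, which the trial report should acknowledge.

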### 4 PATIENT POPULATION

### 4.1 INCLUSION CRITERIA:

- The patient has been implanted with HeartMate 3 LVAS
- The patient is, at a minimum, 3 months post HeartMate 3 implant
- The patient is stable, ambulatory, and has been discharged home
- The patient provides written informed consent before any clinical investigation related procedure

### 4.2 EXCLUSION CRITERIA:

- Non-compliance with anticoagulation and antiplatelet medication, in the opinion of the investigator
- Weight  $\leq$  60 kgs. or age  $\geq$  80 years

- Poor kidney function with serum creatinine ≥ 221umol/L or creatinine clearance < 0.042 mL/s, or the need for chronic renal replacement therapy

- Total bilirubin > 43 umol/L, shock liver, or biopsy-proven liver cirrhosis
- Absence of an informed consent
- Presence of any mechanical prosthetic valve or any ancillary circulatory assist device system (other than the HM3)
- Recent history of cardioembolic stroke
- Hemodynamically significant carotid arteries stenosis (documented by imaging investigation not older than 12 months)
- Need for antiplatelet therapy for reasons other than LVAD therapy
- Major HRAE event after HeartMate 3 index hospitalization discharge
- Known history of hyper- or hypo- coagulable disorder
- Anti-phospholipid syndrome positive patients with documented history of thrombotic/thromboembolic events
- Known hypersensitivity or allergy to apixaban or aspirin
- The patient is involved in another interventional study or any study that could potentially affect the functioning of the HM3 LVAD or the therapeutic effect of any of the study anticoagulants (warfarin, apixaban or aspirin), or could potentially confound the study results
- The patient is currently pregnant, breastfeeding, or intending to get pregnant during the study
- Presence of other anatomic or comorbid conditions, or other medical, social, non-compliance or psychological conditions that, in the investigator's opinion, could limit the subject's ability to participate in the clinical investigation or to comply with follow-up requirements or impact the scientific soundness of the clinical investigation results.

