#### 6.2 ETHICS REVIEW BOARD (ERB)

ERB approval will be obtained prior to enrolling any patients in this study. ERB will maintain oversight of the study in accordance with local policies and procedures.

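### The creatinine-clearance exclusion (< 0.042 mL/s, i.e. 2.52 mL/min) is too low to exclude anyone whom the creatinine, age and weight limits do not already exclude

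*Protocol*

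**What the plan says.** The renal bullet in Protocol section 4.2 offers three alternative grounds for exclusion. It opens with "Poor kidney function with serum creatinine ≥ 221umol/L" and continues with "creatinine clearance < 0.042 mL/s, or the need for chronic renal replacement therapy". The three are joined by 'or', so any one is enough. The preceding bullet removes patients who weigh 60 kg or less or are 80 or older. The last bullet lets the investigator exclude for other comorbid conditions.

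No formula or measurement method for clearance is given. The clearance limit appears once in the protocol and not at all in the SAP.

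Two other places bear on renal function and exposure. Section 3.3.1 says of the 5 mg twice-daily apixaban regimen that it is "dose targeted to renal function", without a cut-off. Section 5.2.4.1 provides for measuring exposure after enrolment: "Apixaban peak and trough levels will be performed using a commercially available anti-Xa assay", at the 4-week visit, with further levels at any HRAE.

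**The concern.** A clearance limit placed beside a creatinine limit normally has a purpose: to catch patients whose creatinine looks acceptable but whose age, sex or weight means that their kidney function is poorer than it suggests. A limit of 2.52 mL/min looks far too low to do that in patients whose creatinine must be below 221 umol/L.

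At stake is an eligibility limit for exposure to the study drug, in a trial whose purpose is safety and feasibility. It matters for more than the 30 patients randomized to apixaban, because sections 3.2 and 3.3.1 move the control arm to apixaban after 180 days. Section 3.1 also leaves the study open to further centers, which would apply the limit as printed.

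**Working it through.** The stated limit has no derivation in the documents, so there is no calculation to reproduce. The check is whether the limit can act.

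**Inputs from section 4.2:** clearance limit 0.042 mL/s; eligible patients have creatinine below 221 umol/L, age below 80 and weight above 60 kg.

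**Assumption:** Cockcroft-Gault, clearance (mL/min) = (140 − age) × weight / (72 × creatinine in mg/dL), times 0.85 for women. Creatinine converts at 88.4 umol/L per mg/dL.

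**Step 1, units.** 0.042 × 60 = 2.52 mL/min. The creatinine limit is 221 / 88.4 = 2.50 mg/dL.

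**Step 2, lowest clearance still eligible.** Clearance falls with higher age, lower weight and higher creatinine, so the minimum lies at the corner of the three limits:

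- Men: (140 − 80) × 60 / (72 × 2.50) = 20.0 mL/min = 0.333 mL/s; 20.0 / 2.52 = 7.9.
- Women: 20.0 × 0.85 = 17.0 mL/min = 0.283 mL/s; 17.0 / 2.52 = 6.7.

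Every eligible patient lies above these values. No limit at or below about 0.283 mL/s can exclude anyone new. For a patient just inside the limits (age 79, 60.1 kg) the figures are 20.4 mL/min for a man and 17.3 for a woman.

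**Step 3, the reverse question.** For clearance to fall to 2.52 mL/min at age 80 and 60 kg, creatinine would have to be 60 × 60 / (72 × 2.52) × 88.4 = 1754 umol/L (men), or 1754 × 0.85 = 1491 umol/L (women). Both are far above 221.

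**Step 4, other estimating equations.** At creatinine 221 umol/L and age 79, MDRD gives 25.0 (men) and 18.6 (women), and CKD-EPI 2009 gives 23.5 and 17.7. These are filtration rates normalized to body surface area, so they are not the same quantity, but they are of the same order and nowhere near 2.52.

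**Step 5, what a working limit would act on.** Over an illustrative range of ages 50 to 79 and weights 60.1 to 90 kg, at creatinine just under 221 umol/L, clearance runs from 20.4 to 45.0 mL/min in men and from 17.3 to 38.3 in women. That is (90/61) × (90/60.1) = 2.2-fold within each sex, and 45.0 / 17.3 = 2.6-fold across both. The clause acts on none of it.

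**Step 6, illustration only: if 0.42 mL/s was meant.** 0.42 × 60 = 25.2 mL/min. The creatinine at which clearance reaches 25.2 is (140 − age) × weight / (72 × 25.2) × 88.4, times 0.85 for women:

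| Age, weight | Man (umol/L) | Woman (umol/L) | Newly excluded below 221? |
|---|---|---|---|
| 79 y, 60.1 kg | 179 | 152 | both |
| 75 y, 65 kg | 206 | 175 | both |
| 70 y, 65 kg | 222 | 188 | women only |
| 60 y, 85 kg | 331 | 282 | neither |

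A tenfold slip would fit: 25 / 60 = 0.417, which rounds to 0.42, and 2.5 / 60 = 0.0417, which rounds to 0.042. This is inference; the documents do not give the intended figure.

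**The case against.** The strongest reply concerns weight, since the arithmetic is not in dispute. The limits on creatinine, renal replacement therapy, age and weight all still operate, as does investigator discretion. The age and weight limits already remove the patients with the lowest clearance at a given creatinine. Kidney function is also followed after enrolment: section 5.2.4 includes it in routine laboratory work, Appendix III records creatinine at regular visits and at events, and kidney dysfunction is a secondary endpoint. The Introduction describes apixaban as the studied factor Xa inhibitor that relies least on the kidneys. The documents do not show that a clearance of about 17 to 25 mL/min is unsafe on this drug.

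All of that stands, and it makes the consequence small. It does not make the clause work. Monitoring and drug levels come after exposure, and dosing by renal function excludes no one.

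Two technical points also deserve an answer. First, a clearance measured by urine collection is not bound by the Cockcroft-Gault algebra, so redundancy is proved only under that formula. A measured value below 2.52 mL/min with creatinine under 221 umol/L is nevertheless implausible in a stable, ambulatory patient. Second, the point rests on one decimal place, so the figure should be confirmed against the signed protocol page. Nothing in the text suggests that the digits or unit are garbled.

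**Conclusion.** The concern holds. As printed, the limit is 2.52 mL/min. Under Cockcroft-Gault it would have to be about 6.7 times higher (0.283 / 0.042) before it could exclude even the most extreme patient whom the other limits allow. A decimal or unit error is very likely; the intended value is unknown.

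What is lost is a limit that combines creatinine with age, weight and sex. The patients concerned are mainly older and lighter, women more than men, with creatinine near but below 221 umol/L. The documents do not show how many of the 45, if any, are in that group. The primary endpoint, the comparison of arms and the analysis do not change. It should be fixed because it is a safety threshold that is wrong as written and nothing else in the documents corrects it.

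**What to change.** The sponsor should confirm and correct the clearance limit in section 4.2, give it in both mL/s and mL/min, and name the formula or method. The value is the sponsor's to state. The change goes through an amendment under the oversight described in section 6.2: "ERB will maintain oversight of the study in accordance with local policies and procedures".

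Optionally, patients already enrolled can be checked against the corrected limit, for safety review only, from the baseline creatinine, weight, sex and date of birth already collected. They remain eligible under the text in force when they enrolled.

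The cost is one figure and a named formula. The SAP does not restate the renal limits and can stay as it is. The optional check covers at most 45 patients. The only downside is possibly a few more exclusions at screening.

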### 5 STUDY COURSE

### 5.1 ENROLLMENT PROCEDURES

Patients will sign an informed consent form at the time of the study enrollment. The consent form states that the data collected for this study will be used by authorized personnel only. The patient's privacy will be maintained according to local legislation and, patients will be identified by study specific code. The aggregate and/or de-identified patient specific data may be published or presented.

